18 ADMINISTRATIVE AND ETHICAL CONSIDERATIONS

18.1 Regulatory and Ethical Compliance

This protocol was designed and will be conducted and reported in accordance with the International Conference on Harmonization (ICH) Harmonized Tripartite Guidelines for Good Clinical Practice, the Declaration of Helsinki, and applicable federal, state, and local regulations.

18.2 DUHS Institutional Review Board and DCI Cancer Protocol Committee

The protocol, informed consent form, advertising material, and additional protocol-related documents must be submitted to the DUHS Institutional Review Board (IRB) and DCI Cancer Protocol Committee (CPC) for review. The study may be initiated only after the PI has received written and dated approval from the CPC and IRB.

The PI must submit and obtain approval from the IRB for all subsequent protocol amendments and changes to the informed consent form. The CPC should be informed about any protocol amendments that potentially affect research design or data analysis (i.e. amendments affecting subject population, inclusion/exclusion criteria, agent administration, statistical analysis, etc.).

The PI must obtain protocol re-approval from the IRB within 1 year of the most recent IRB approval. The PI must also obtain protocol re-approval from the CPC within 1 year of the most recent IRB approval, for as long as the protocol remains open to subject enrollment.

18.3 Informed Consent

The informed consent form must be written in a manner that is understandable to the subject population. Prior to its use, the informed consent form must be approved by the IRB.

The PI or authorized key personnel will discuss with the potential subject the purpose of the research, methods, potential risks and benefits, subject concerns, and other study-related matters. This discussion will occur in a location that ensures subject privacy and in a manner that minimizes the possibility of coercion. Appropriate accommodations will be made available for potential subjects who cannot read or understand English or are visually impaired. Potential

subjects will have the opportunity to contact the PI or authorized key personnel with questions, and will be given as much time as needed to make an informed decision about participation in the study.

Before conducting any study-specific procedures, the PI must obtain written informed consent from the subject or a legally acceptable representative. The original informed consent form will be stored with the subject's study records, and a copy of the informed consent form will be provided to the subject. The PI is responsible for asking the subject whether the subject wishes to notify his/her primary care physician about participation in the study. If the subject agrees to such notification, the Principal Investigator will inform the subject's primary care physician about the subject's participation in the clinical study.

18.4 Data and Safety Monitoring

Data and Safety Monitoring will be performed in accordance with the DCI Data and Safety Monitoring Plan (DSMP). For a more detailed description of the DSMP for this protocol, refer to Sections 16.3 and Section 17.1.

18.5 Protocol Amendments

All protocol amendments must be initiated by the PI and approved by the IRB prior to implementation. IRB approval is not required for protocol changes that occur to protect the safety of a subject from an immediate hazard. However, the PI must inform the IRB and all other applicable regulatory agencies of such action immediately.

Though not yet required, the CPC should be informed about any protocol amendments that potentially affect research design or data analysis (i.e. amendments affecting subject population, inclusion/exclusion criteria, agent administration, etc.).

18.6 Publication Plan

The results will be made public within 24 months of reaching the end of the study. The end of the study is the time point at which the last data items are to be reported, or after the outcome data are sufficiently mature for analysis, as defined in the section on Sample Size, Accrual Rate and Study Duration. A report is planned to be published in a peer-reviewed journal, thus the initial release may be an abstract that meets the requirements of the International Committee of Medical Journal Editors. A full report of the outcomes is planned to be made public no later than three (3) years after the end of the study.

19 Privacy, Confidentiality, and Data Storage

The PI will ensure that subject privacy and confidentiality of the subject's data will be maintained. Research Data Security Plans (RDSPs) will be approved by the appropriate institutional Site Based Research group.

To protect privacy, every reasonable effort will be made to prevent undue access to subjects during the course of the study. Prospective participants will be consented in an exam room where it is just the research staff, the patient and his family, if desired. For all future visits, interactions with research staff (study doctor and study coordinators) regarding research activities will take place in a private exam room. All research related interactions with the participant will be conducted by qualified research staff who are directly involved in the conduct of the research study.

To protect confidentiality, subject files in paper format will be stored in secure cabinets under lock and key accessible only by the research staff. Subjects will be identified only by a unique study number and subject initials. Electronic records of subject data will be maintained using a dedicated database (MediData RAVE) which is housed in an encrypted and password-protected, DCI file server. Access to electronic databases will be limited to authorized key personnel only. Subject data may be stored temporarily on encrypted and password-protected portable memory devices such as flash drives and external hard drives, but only when absolutely necessary. Data stored on portable memory devices will be de-identified. Subject data will be deleted from the portable memory device at the earliest opportunity. The security and viability of the IT infrastructure will be managed by the DCI and/or Duke Medicine.

Upon completion of the study, research records will be archived and handled per DUHS HRPP policy.

Subject names or identifiers will not be used in reports, presentations at scientific meetings, or publications in scientific journals.

20 Data Collection and Maintenance

20.1 Study Documentation

Study documentation includes but is not limited to source documents, case report forms, monitoring logs, appointment schedules, study team correspondence with PI-sponsor or regulatory bodies/committees, regulatory documents that can be found in the DCI-mandated "Regulatory Binder", which includes but is not limited to signed protocol and amendments, approved and signed informed consent forms, FDA Form 1572, CAP and CLIA laboratory certifications and clinical supplies receipts and distribution records (if applicable).

Source documents are original records that contain source data, which is all information in original records of clinical findings, observations, or other activities in a clinical trial necessary for the reconstruction and evaluation of the trial. Source documents include but are not limited to hospital records, clinical and office charts, laboratory notes, memoranda, subjects' diaries or evaluation checklists, pharmacy dispensing records, recorded data from automated instruments, copies or transcriptions certified after verification of being accurate copies, microfiches, photographic negatives, microfilm or magnetic media, x-rays, subject files, and records kept at the pharmacy, at the laboratories and at medico-technical departments involved in the clinical trial. When possible, the original record should be retained as the source document. However, a photocopy is acceptable provided that it is a clear, legible and exact duplication of the original document.

The research nurse, research coordinator, data manager and PI are responsible for ensuring that data extraction (information required by the protocol) is completed in a timely manner for every patient enrolled on study. The following forms are an integral part of the study data and will be maintained in the patients' clinical or research chart in accordance with the institutions practice. Any errors on the forms should be lined through, but not obliterated with the correction inserted, initialed and date by the person making the correction

- Eligibility checklist
- Serious and non-serious adverse event forms (if applicable)
- Protocol Deviation Form (if applicable)

20.2 Case Report Forms (CRFs)

The electronic CRF will be the primary data collection document for the study. The CRFs will be updated within two weeks of acquisition of new source data. The electronic records of subject data will be maintained using a dedicated database (Medidata Rave and/or Redcap) which is housed in an encrypted and password protected DCI file server. Access to electronic databases will be limited to the PI and designated study staff listed on key personnel. Subject data may be stored temporarily on encrypted and password-protected portable memory devices such as flash drives and external hard drives, but only when absolutely necessary. Data stored on portable memory devices will be de-identified. Subject data will be deleted from the portable memory device at the earliest opportunity. The security and viability of the IT infrastructure will be managed by the DCI and/or Duke Medicine. Only approved study staff, are permitted to make entries, changes, or corrections in the CRF.

An audit trail will be maintained automatically by the electronic CRF management system (Medidata Rave and/or Redcap). Designated personnel will complete user training, as required or appropriate per regulations

20.3 Data Management Procedures and Data Verification

Designated personnel using the electronic CRF will have access based on their specific roles in the protocol.

Completeness of entered data will be checked automatically by the eCRF system, and users will be alerted to the presence of data inconsistencies. Additionally, the data manager will cross-reference the data to verify accuracy. Missing or implausible data will be highlighted for the PI requiring appropriate responses (i.e. confirmation of data, correction of data, completion or confirmation that data is not available, etc.).

The database will be reviewed and discussed prior to database closure, and will be closed only after resolution of all remaining queries. An audit trail will be kept of all subsequent changes to the data.

21 Study Closure

Following completion of the studies, the PI will be responsible for ensuring the following activities:

- Data clarification and/or resolution
- Accounting, reconciliation, and destruction/return of used and unused study drugs
- Review of site study records for completeness
- Shipment of all remaining laboratory samples to the designated laboratories

Upon completion of the study, research records will be archived and handled per DUHS (or participating Institution's) HRPP policy.

21.1 Records Retention

The Principal Investigator will maintain study-related records for the longer period of:

- At least two years after the date on which a New Drug Application is approved by the FDA (if an IND is involved).
- At least two years after formal withdrawal of the IND associated with this protocol (if an IND is involved).
- At least six years after study completion (Duke policy).

22 STATISTICAL METHODS AND DATA ANALYSIS

22.1 Analysis Sets

The efficacy and safety analysis set consists of all patients who receive at least one dose of osimertinib and it will be used to analyze safety and efficacy endpoints, including objective response rate, progression-free survival and overall survival. Patients who withdraw prior to study treatment or fail to receive study treatment for various reasons, will not be included in the efficacy and safety analysis.

22.2 Patient Demographics and Other Baseline Characteristics

Standard demographic information (age, gender, etc.) and prior therapies, smoking history and specific mutation type will be collected.

22.3 Study Treatments

Osimertinib 80 mg daily until disease progression, unacceptable toxicity or withdraw of consent.

22.4 Primary Objective

Objective response rate, defined as all patients with a confirmed partial or complete response as assessed by investigator using RECIST 1.1

22.4.1 Variable

The primary outcome will be objective response rate as assessed by the investigator using RECIST 1.1 (appendix 3). Patients with confirmed partial or complete responses will be considered responders and patients without a partial or complete response will be considered non-responders.

22.4.2 Statistical Hypothesis, Model, and Method of Analysis

The single-arm phase II trial is designed to test the following hypothesis about the anti-tumor activity of the experimental therapy:

$$H_0: ORR \leq 20\% \text{ versus } H_1: ORR \geq 40\%,$$

where ORR is the true ORR for the experimental therapy. We will use Simon's optimal 2-stage design to evaluate the ORR.²⁷ The 2-stage design allow a futility test after stage

I patients has been evaluated for tumor response. The specific design described below is also the design that yields the smallest expected sample size under the null hypothesis (optimal) among all designs satisfying type I error of 0.10 and type II error of 0.10.

Specifically, the first stage will enroll 17 patients. If there are 3 or fewer patients confirmed responders (complete or partial response) among the 17 patients, the trial will be terminated; otherwise, the trial will move forward to enroll additional 20 patients. If 10 or fewer patients among the total of 37 patients are confirmed responders, the experimental therapy will be concluded as not worthy of further investigation; otherwise it will be conducted that the experimental therapy has sufficient activity worthy of further investigation. The above design has expected sample size 26 under the null hypothesis. The early stopping probability at stage I is 0.5489 under the null hypothesis. The actual type I and type II errors are 0.0948 and 0.0967, respectively.

Patient characteristics at baseline will be summarized in tables and graphs. Categorical data will be summarized using frequency tables while summary statistics such as means, medians, standard deviation, range, etc. will be provided for continuous data.

All enrolled patients, except for those withdrawn prior to study treatment or fail to receive study treatment for various reasons, will be included in the efficacy analysis. The primary endpoint will be objective response rate (ORR) per RECIST 1.1. Patients with confirmed partial or complete responses will be considered responders and patients without a confirmed partial or complete response will be considered non-responders. Patients who stop therapy prior to confirmation of response per RECIST will be considered non-responders. Patients who are not able to get radiographic assessment for all reasons will be considered non-responders. At the end of the trial, the ORR will be estimated using the UMVUE method, and the p-value and 95% confidence interval will calculated.^{28,29}

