The current standard first-line therapy is a platinum doublet for patients with stage 4 disease and uncommon *EGFR* mutations. Platinum and pemetrexed has an objective response rate (ORR) of approximately 30% and a median PFS 4 to 5 months in patients with an *EGFR* mutation.^{18,23} The standard second-line therapies are immunotherapy and docetaxel. A response rate of approximately 5-10% and median PFS of approximately 3 months are observed with docetaxel, and with immunotherapy a response rate of 20% is observed in the intent-to-treat patient population. The response rate is estimated to be lower in the *EGFR* mutant patient population.^{13-15,24} In subset analyses of phase 3 trials of immunotherapy compared to docetaxel a survival benefit was not observed with immunotherapy in the *EGFR* mutation subset.¹³⁻¹⁵ A higher mutational burden and a history of smoking is associated with benefit from immunotherapy, and patients with *EGFR* mutant NSCLC have lower mutational burden and frequently a history of never smoking or light smoking.²⁵ These clinical and biomarker data have raised questions about the activity of immunotherapy in patients with *EGFR* mutant NSCLC.

Recently the second and third-line approval of erlotinib was rescinded by the FDA. Afatinib is approved in the second-line setting only for squamous histology NSCLC. This limits the availability of EGFR TKIs in the second-line setting for patients with *EGFR* mutations besides the exon 19 deletions and exon 21 L858R mutation. Thus, there are limited effective options for patients with uncommon *EGFR* mutations.

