5.2 Exclusion Criteria

Patients will be excluded from the study if they meet **any** of the following criteria:

1. Prior therapy with EGFR TKI therapy
2. Greater than 2 lines of prior systemic therapy for metastatic non-small cell lung cancer.
3. Any cytotoxic chemotherapy or other anticancer drugs from previous treatment regimen or clinical study within 14 days of first dose of study drug.
4. Treatment with an investigational drug within 5 half-lives of the compound
5. Other active malignancy \leq 2 years prior to study enrollment. EXCEPTIONS: Non-melanotic skin cancer or carcinoma-in-situ of the cervix. NOTE: If there is a history of prior malignancy, patients must **not** be receiving other specific treatment (i.e. hormonal therapy) for their cancer
6. Prior radiotherapy \leq 14 days
7. Untreated symptomatic brain metastases (treated brain metastases are allowed provided $>$ 14 days have elapsed from completion of radiotherapy and patient is neurologically stable as assessed by treating physician).
8. Malabsorption syndrome, refractory nausea and vomiting, chronic gastrointestinal diseases, inability to swallow the formulated product or previous significant bowel resection that would preclude adequate absorption of osimertinib
9. Detection of concurrent *EGFR* mutation with exon 20 T790M, exon 19 deletion, exon 21 L858R mutation or exon 20 insertion. Patients with compound (also referred to as multiple mutations) will be excluded if the molecular testing includes one of these mutations
10. Active pregnancy or breast-feeding: Pregnant women are excluded from this study because the effects of osimertinib on the development of the fetus are unknown, and there is potential for teratogenic or abortifacient effects. Because there is an unknown but potential risk for adverse events in nursing infants secondary to treatment of the mother with osimertinib, breastfeeding should be discontinued if the mother is treated with these agents.
11. Grade \geq 2 blurred vision, conjunctivitis, corneal ulcer, dry eye, or keratitis
12. Men who intend to father children during the study or within 4 months afterward are excluded
13. Major surgery within 4 weeks of first dose of study drug.

14. Any unresolved toxicities from prior therapy greater than CTCAE grade 1 at the time of starting study treatment, with the exception of alopecia or neuropathy

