22.5.3 Statistical Analysis for Secondary Objectives

Patients who are not able to get radiographic assessment for all reasons will be considered disease progression at the time they discontinue protocol therapy for the PFS analysis. Patients who stop therapy for reasons other than disease progression will be followed for disease progression. Patients who have not experienced an event of interest by the time of analysis will be censored at the date they are last known to be alive and progression-free. Overall survival is defined as the time from start of study therapy to death from any cause, and patients who are alive at the time of analysis will be censored at the last date of contact. Time to event endpoints will be summarized using the method of Kaplan and Meier as well as by Cox regression in the presence of covariates. Potential co-variates including smoking history, mutation subtype, gender, and performance status.

An exploratory subset analysis will estimate the objective response rate, PFS and OS in the specific mutation subsets of exon 18 G719X, exon 20 S7681, exon 21 L861Q or compound mutations.

The evaluation of safety using the AE using NCI CTCAE version 4.03. All patients who receive at least one dose of study treatment will be included in the safety analysis.

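### Does a positive decision at 11 of 37 responders conflict with the planned 95% confidence interval and with the 30% response rate cited for chemotherapy?

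*Combined protocol and SAP*

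**What the plan says.** Section 22.4.2 sets a null ORR of 20% or less against an alternative of 40% or more. It chooses the design with the smallest expected sample size under the null "among all designs satisfying type I error of 0.10 and type II error of 0.10". On the plan, "the first stage will enroll 17 patients", and the trial stops if three or fewer respond. Otherwise 20 more patients enter. "If 10 or fewer patients among the total of 37 patients are confirmed responders", the therapy is dropped; with 11 or more it is judged active enough to study further.

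For reporting, the same section says "the ORR will be estimated using the UMVUE method, and the p-value and 95% confidence interval will calculated". It cites two papers for the method and does not state whether the p-value and interval are one-sided or two-sided.

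On benchmarks, the current-therapy text of Section 2.1 says "Platinum and pemetrexed has an objective response rate (ORR) of approximately 30% and a median PFS 4 to 5 months" in patients with an EGFR mutation. For second-line treatment it gives 5-10% with docetaxel and 20% with immunotherapy, the latter expected to be lower in EGFR-mutant disease. Section 5.2 excludes "Greater than 2 lines of prior systemic therapy for metastatic non-small cell lung cancer", so patients with none, one or two prior lines may enter. Section 22.2 collects prior therapies. Section 22.5.3 lists "Potential co-variates including smoking history, mutation subtype, gender, and performance status" and plans subsets by mutation only.

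**The concern.** Two things look out of line.

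First, the test spends 10% in one tail, while a two-sided 95% interval spends 2.5%. For some response counts the report would call the drug sufficiently active and print beside that an interval that includes the rate the trial set out to exclude.

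Second, the plan gives no source for the 20% null. It equals the immunotherapy rate quoted for second-line use, yet untreated patients are eligible and the chemotherapy rate quoted in the first-line text is about 30%. The smallest positive count, 11/37 = 29.7%, is no higher than that. Prior therapy is collected but is not named among the covariates or subsets, so a reader could not match the result to the relevant benchmark.

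The trial is meant to inform whether a larger study should follow. If both points held, such a study could be launched on a result that neither excludes the null nor improves on chemotherapy.

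**Working it through.** **Inputs** (Section 22.4.2): n1 = 17, stop at 3 or fewer; n2 = 20, total 37; positive at 11 or more; null 0.20, alternative 0.40. Assumption: the 95% interval is two-sided with equal tails and uses the exact two-stage distribution.

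**1. The plan's own figures.** With X1 ~ Bin(17, p) and X2 ~ Bin(20, p),

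P(positive | p) = Σ over x = 4 to 17 of P(X1 = x) · P(X2 ≥ 11 − x).

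| Quantity | Plan | Recomputed |
|---|---|---|
| P(X1 ≤ 3) at p = 0.20 | 0.5489 | 0.5489 |
| Expected N = 17 + 20 × (1 − 0.5489) | 26 | 26.02 |
| Type I error, P(positive) at 0.20 | 0.0948 | 0.0948 |
| Type II error, 1 − P(positive) at 0.40 | 0.0967 | 0.0967 |

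A search over two-stage designs with up to 55 patients returns this same design as optimal.

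**2. What would be reported near the boundary.** For a total of s responders after continuing past stage 1:

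- UMVUE = Σ C(16, x−1)·C(20, s−x) / Σ C(17, x)·C(20, s−x), with x from 4 to s. At s = 11 this is 236,198,340 / 743,181,180 = 0.318.
- The one-sided p-value is P(continue and total ≥ s | p = 0.20).
- The lower limit is the p at which P(continue and total ≥ s | p) equals 0.025 (95% interval) or 0.10 (80% interval). The upper limit comes from the opposite tail in the same way.

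| Responders | Raw ORR | UMVUE | One-sided p | 95% interval | 80% interval |
|---|---|---|---|---|---|
| 10 | 27.0% | 30.0% | 0.163 | 14.2–46.1% | 18.1–39.8% |
| 11 | 29.7% | 31.8% | 0.095 | 16.1–48.0% | 20.2–42.1% |
| 12 | 32.4% | 33.8% | 0.049 | 18.2–50.3% | 22.4–44.5% |
| 13 | 35.1% | 36.0% | 0.022 | 20.3–52.8% | 24.7–47.1% |

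The 95% interval includes 20% at 11 and 12 and first excludes it at 13. At 11, Clopper-Pearson (15.9–47.0%), Wilson (17.5–45.8%) and Wald (15.0–44.5%) intervals also include 20%. The 80% interval, with 10% in each tail, excludes 20% at 11 and includes it at 10, exactly where the decision changes.

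**3. How often it would happen.**

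| True ORR | P(positive) | P(11 or 12) | Share of positives |
|---|---|---|---|
| 20% | 0.095 | 0.072 | 76% |
| 30% | 0.540 | 0.245 | 45% |
| 40% | 0.903 | 0.135 | 15% |
| 50% | 0.991 | 0.018 | 2% |

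At a true 30% the chance of stopping at stage 1 is P(X1 ≤ 3) = 0.20.

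**4. What forcing agreement would cost.** Keeping stage 1 and requiring 13 of 37, so that every positive result has a 95% interval above 20%, gives type I error 0.022 and power 0.903 − 0.135 = 0.769 at 40%. Moving the test to 30% versus 50% with the same numbers of patients (stop at 5 or fewer of 17, positive at 15 or more of 37) gives type I error 0.099 and power 0.869 at 50%. Its type II error is 1 − 0.869 = 0.131, above the plan's limit of 0.10, and power at 40% drops to 0.489.

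**The case for a change.** The best case for a change does not need an arithmetic error. The section does not say which output governs the conclusion or whether the p-value is one-sided, and at a true 30% almost half of the positive results would show a 95% interval that includes 20%. The 20% null has no stated rationale in a population of mixed treatment lines. A drug only as active as the cited chemotherapy would pass 54% of the time. Stating the sidedness, adding an 80% interval and tabulating ORR by prior therapy would cost almost nothing.

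The observations are correct, but they do not make the plan unsound.

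- **The interval.** The only criterion in Section 22.4.2 is the response count, and the hypotheses run in one direction at a 10% error rate. The one-sided p-value of 0.095 agrees with a positive result at 11. An 80% interval would show this more directly, but it changes neither the estimate nor the decision.
- **The chemotherapy rate.** The estimate to be reported at 11 is the UMVUE, 31.8%, not 29.7%, although neither can be told apart from 30%. The two sources that Section 2.1 cites for the 30% are, by their titles in Section 23, a trial in T790M-positive disease and a trial after progression on gefitinib. Section 5.2 excludes both T790M and prior EGFR TKI. The 30% is therefore a loose benchmark for this population.
- **The pass rate at 30%.** A value of 54% is what one expects halfway between a 20% null and a 40% alternative.
- **Prior therapy.** The covariate list is worded as open and serves the time-to-event models. The data are collected, so an analyst can tabulate ORR by prior line without an amendment, and in at most 37 patients that table would be exploratory.

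What stands is that the text is terse: the sidedness and the reason for 20% are left to the reader.

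**Conclusion.** No change to the plan is needed. The design is computed correctly, and the decision and the interval differ because they use different error levels, not because they disagree about the data. With 11 or 12 responders the report would pair a positive decision with a 95% interval that includes 20%. The probability of that is 7%, 25% and 13% at true rates of 20%, 30% and 40%, and about 2% at 50%. A reader who knows that the test is one-sided at 10% can interpret the pair correctly.

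A positive result supports activity above 20% and nothing stronger. That null lies within the 5% to 30% cited in Section 2.1 for the lines of therapy that may enter. Making the 95% interval decisive would reduce power at 40% from 90% to 77%, and moving to 30% versus 50% would reduce it to 49%. Keeping the present boundaries is a fair choice for a phase 2 screen.

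This rests on reading the 95% interval as two-sided with equal tails and the p-value as one-sided, in line with the hypotheses.
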